1.0 Background

- 1.1 Treatment
 - 1.11 Therapy for Pancreatic Cancer

While the treatments for metastatic pancreatic cancer have improved in the last decade, and modern chemotherapy regimens, including FOLFIRINOX and gemcitabine + nab-paclitaxel have improved survival times, the hard reality is that the vast majority of patients do not respond to standard chemotherapy. Specifically, the objective response rate (ORR) with front line FOLFIRINOX or gemcitabine + nab-paclitaxel are 32% and 23% respectively (Conroy et al, 2011; Von Hoff et al, 2013). In the 2nd line setting, those percentages drop considerably. For patients treated with the only FDA-approved second line therapy regimen, 5-flurouracil + nano-liposomal irinotecan, the ORR is only 17%, and the median progression-free (PFS) and overall survival (OS) was only 4 and 6 months, respectively (Wang-Gillam et al, 2016). Multiple other Phase II trials as 2nd line therapy for patients have yielded ORR of 2.5 to 24%, with a PFS typically of 2 - 4 months, and OS typically of 4 - 6 months (Boeck *et al*, 2008; Boeck et al, 2007; Cantore et al, 2004; Cereda et al, 2016; Cereda et al, 2011; Demols et al, 2006; Kim et al, 2012; Milella et al, 2004; Oettle et al, 2000; Tsavaris et al, 2005; Ulrich-Pur et al, 2003; Xiong et al, 2008; Zaniboni et al, 2012).

1.12 Predictive Biomarkers in Pancreatic Cancer, and BRAF mutations

There are no FDA approved targeted therapies for patients with pancreatic cancer. However, broad-based genetic sequencing efforts have consistently revealed that $\geq 25\%$ of pancreatic cancers have potentially highly actionable molecular biomarkers with the definition of "highly actionable" being identified as a biomarker that predicts for a high response rate, or otherwise high degree of clinical activity for a therapy targeted to that biomarker, as defined in any cancer type (Aguirre *et al*, 2018; Bailey *et al*, 2016; Biankin *et al*, 2012; Collisson *et al*, 2011; Lowery *et al*, 2017; Pishvaian *et al*, 2018; Waddell *et al*, 2015; Witkiewicz *et al*, 2015). Two biomarkers that are clearly linked to a high degree of anti-cancer activity across tumors types include MSI-high or MMR deficient solid tumors, and NTRK fusions. Pembrolizumab and nivolumab are FDA approved for MSI-high or MMR deficient solid tumors (Le *et al*, 2015); while larotrectinib is FDA approved for tumors that harbor NTRK gene fusions (Drilon *et al*, 2018).

One such predictive biomarker is an activating mutation in the *BRAF* gene. In the population of pancreatic cancers lacking *KRAS* mutations, probable driver mutations have been identified including *BRAF*, *GNAS*, *CTNNB1*, as well as NRG1 fusions (Cancer Genome Atlas Research Network. Electronic address & Cancer Genome Atlas Research, 2017; Heining et al, 2018). *BRAF* mutations specifically have been previously identified in *KRAS* wild-type and mutant pancreatic cancer cell lines and patient tumors (Foster et al, 2016; Ishimura et al, 2003; Singhi et al, 2019).

BRAF alterations have also been identified in multiple cancer types including lung, colon, thyroid, and melanoma, as well as in non-Hodgkin lymphoma

(Davies *et al*, 2002; El-Osta *et al*, 2011). In pancreatic acinar cell carcinomas, rearrangements involving BRAF and RAF1 (CRAF) have been identified in approximately 23% of tumors (Chmielecki *et al*, 2014). Combined BRAF and MEK inhibition is now FDA approved for metastatic melanoma, non-small cell lung cancer and anaplastic thyroid cancer. In addition, targeting BRAF^{V600} alterations with combinations of RAF/MEK inhibition with and anti-EGFR therapy has improved outcomes in colorectal cancer (Hyman *et al*, 2015; Planchard *et al*, 2016; Van Cutsem *et al*, 2019) and received breakthrough FDA status in 2018.

These alterations have been recently classified into 3 functional classes based on dependence of RAS activation, BRAF kinase activity, and signaling properties (Yaeger & Corcoran, 2019). Class I BRAF mutations result in RAS-independent kinase activation and signal as monomers (Poulikakos *et al*, 2010; Pratilas *et al*, 2009). To date, this class typically includes BRAF^{V600E} mutations. Class II mutations are also RAS-independent but signal as heterodimers and do not commonly co-occur with other alterations in the MAPK pathway (Yao *et al*, 2015). This group includes activating *BRAF* mutations, several fusions, and inframe deletions. Class III mutations are RAS-dependent and occur when these mutations heterodimerize with wild-type CRAF and amplify Ras signaling. Class III mutations often co-occur with activating *RAS* mutations, or NF1 loss-offunction mutations.

We recently evaluated several large pancreatic cancer next-generation sequencing (NGS) datasets, and we identified four categories of BRAF alterations: $BRAF^{V600}$ mutations, other missense mutations, in-frame deletions, and fusions all of which were evenly represented across patients (Table 1). Acinar cell carcinomas frequently harbored BRAF fusions (4/6, 67%); while patients with neuroendocrine tumors most frequently had $BRAF^{V600}$ mutations and non-canonical BRAF mutations (8/9, 89%). BRAF^{V600E} mutations were also found in rare histologies, with one in a pancreatoblastoma and one in a solid and pseudopapillary neoplasm. The most common BRAF alterations in pancreatic acinar cell cancer patients were BRAF fusions (12/53), in-frame deletions (11/53, N486 P490del, Δ NVTAP) and the canonical $BRAF^{V600}$ mutation (11/53).

Histology	Dataset	#Altered /	Fraction	Alterations
Pancreatic adenocarcinoma	GENIE	13 / 587	0.022	N486_P490del (4); V600_K601delinsE (2); Y633H; *767Cext*3; V600E; L485F; D391N; G469S; H766Y
	ICGC	4 / 572	0.007	V471I; V487S; P334L; D594G
	КҮТ	23 / 926	0.026	N486_P490del (6); V600E (4); SND1- BRAF fusion (3); V600_K601>E; deletion exons 2-10 + S467L; G596R; T310I; MKRN1-BRAF fusion; TMEM9-BRAF fusion; V600E + deletion exons 2-10 (after developing resistance to BRAF-targeted therapy); G469A; rearrangement; D594G; V487_P492>A
	MSK	7 / 383	0.018	BRAF-SND1 fusion (2); BRAF-LUC7L2 fusion; V600R; V600E; BRAF-JHDM1D fusion; V600E + BRAF-SND1 fusion
	TCGA	3 / 150	0.02	T488_Q493delinsK; N486_P490del; R462T
	UTSW	3 / 109	0.028	V600E (3)
	Total	53 / 2,727	0.019	
Pancreatic acinar cell carcinoma	GENIE	3 / 11	0.273	X327_splice; V600E; GLI2-BRAF fusion
	MSK	3 / 13	0.231	BRAF-SND1 fusion (2); GIPC2-BRAF fusion
	Total	6 / 24	0.25	
Pancreatoblastoma	KYT	1 / 1	1	V600E
Solid pseudopapillary neoplasm	GENIE	1 / 7	0.143	V600E

Table 1. BRAF alterations in pancreatic cancers

1.13 BRAF Mutant Cell Lines are Responsive to MEK and RAF Inhibitors NIH/3T3 cells with stable expression of either $BRAF^{V600E}$ or $BRAF^{\Delta^{NVTAP}}$ were treated with varying concentrations of vemurafenib (BRAF^{V600E} inhibitor), PLX8394 (BRAF inhibitor), LY300912 (pan-RAF inhibitor), trametinib (MEK inhibitor), or dabrafenib (BRAF inhibitor) and analyzed for ERK phosphorylation (Figure 1). All of the RAF and MEK inhibitors demonstrates significant single agent activity in the $BRAF^{V600E}$ mutant cell lines (Figure 1C). In the $BRAF^{\Delta^{NVTAP}}$ mutant lines, there appeared to be decreased sensitivity to vemurafenib and LY300912, and otherwise anti-tumor activity across other RAF and MEK inhibitors.

Cell viability studies of BA/F3 populations expressing $BRAF^{V600E}$ or $BRAF^{\Delta NVTAP}$ were performed with varying concentrations of different RAF or MEK inhibitors

(Figure 1, E-H). These studies confirmed single agent activity across the RAF and MEK inhibitors, again with enhanced activity of the $BRAF \Delta^{NVTAP}$ mutant to all treatments.

Figure 1. BRAF Mutant Cell Lines are Responsive to MEK and RAF Inhibitors. (A) Western blot analysis from stable expression of the indicated *BRAF* mutants in NIH/3T3 and BA/F3 cells. The mutants include *BRAF* ^{V600E} and *BRAF* Δ^{NVTAP} . (B) BA/F3 cell growth curve from stable expression of the indicated constructs including control vector, *KRAS*^{G12V}, *BRAF*^{WT}, *BRAF* ^{V600E}, and *BRAF* Δ^{NVTAP} . (C) Western blot of lysates from NIH/3T3 cells with *BRAF* ^{V600E} or *BRAF* Δ^{NVTAP} after treatment with the indicated concentration of different RAF or MEK inhibitors for 2 hours. (D – H) Viability of BA/F3 populations with *BRAF* ^{V600E} or *BRAF* Δ^{NVTAP} after 72 hour treatment with the indicated concentration of different RAF

1.14 A retrospective case series of BRAF mutated pancreatic cancer

In a retrospective case series of pancreatic cancer patients with clinically annotated data, we identified 81 patients with BRAF alterations (Table 1). The histologies were as follows: 65/81 adenocarcinoma, 13/81 acinar cell cancer or mixed acinar/neuroendocrine, 4/81 IPMN and 1 pancreaticoblastoma. Median age was 64 (42 – 86) and 40/81 were women. 69 of the 81 patients (85%) were KRAS wild-type. 18/81 of patients had a V600E, 19/81 non-canonical, 20/81 deletion, and 25/81 fusion abnormalities. The majority of the cohort presented with advanced disease 61/81 (75%) and 20/81 (25%) presented with earlier stage disease. The median overall survival of the cohort was 1.92y [95%CI=1.36-2.44]. The median number of lines of therapy was 2.

In our 81 patients with BRAF alterations, KRAS alterations were only found in 12 (15%) patients. Additional genomic alterations involving the targeted genes of the various sequencing panel were identified in genes such as *TP53* (43%), *CDKN2A/B* (36%), and *SMAD4* (19%).

Of the patients with $BRAF^{V600E}$ alterations, 15/18 were in pancreatic

adenocarcinomas and 3/18 in acinar cell tumors, median age was 63, and 13/17 were women. One had a *KRAS*^{G12V} alteration and 9 had alterations in p53, and 5 alterations in CDKN2A and 4 with alterations in SMAD4.

We then classified these alterations into functional categories using available literature regarding their activity and their response to BRAF targeted therapy. Of the 17 *BRAF*^{V600E} alterations, 13 were placed in class 1 (13/17). If there were additional alterations in BRAF, KRAS, or other potential driving alterations they were placed in class 3 (4/17). In our cohort, co-existing alterations occurred in *NTRK*^{fusion}, *KRAS*^{G12V}, *BRAF*^{Q609L}, and *SND1-BRAF*^{fusion}. Class 2 alterations included fusion abnormalities and in-frame deletions which were placed in separate categories. Our last category included Class 3 alterations, and those with multiple driver mutations. Of those with multiple drivers outside of the BRAF gene, 13/15 were KRAS alterations an NTRK fusion, and a RAF mutation. 3 patients had 2 alterations in the BRAF gene; BRAF^{V600E} + SND-1-BRAF^{Fusion}, BRAF^{V600E} + BRAF^{Q609L}, and BRAF^{S467L} + Exon 2-10^{deletion}.

An overall survival analysis was performed for each of these functional BRAF categories. Patients with IPMN's and resected disease were excluded. Class 1 median overall survival was 1.3 years (N=8); Class 2 (fusion) was 1.9 years (N=18) and Class 2 (non-fusion) was 1.2 (n=12); and class 3 1.6 years (n=15). There were no significant differences found between these categories of BRAF alterations.

1.15 MEK and RAF inhibitors have activity in the patients with KRAS wild-type and BRAF-mutated pancreatic cancers

In our case series, 17 patients were treated with BRAF directed therapy (Figure 2). This includes 6 patients treated with combination BRAF and MEK and 8 patients with MEK inhibitor therapy alone. 2 patients were treated with pan-RAF inhibitors. The median lines of previous therapy was 2 (1-4). In evaluable patients, median weeks of therapy was 21 (7-110).

Responses to BRAF targeted therapy were evaluated based the recently described functional classification system previously described. All patients with Class-1 alterations had significant responses to BRAF targeted therapy. This included 2 BRAF^{*V600E*} alterations with durable partial responses of 48 weeks and over 2 years and in 1 patient with $BRAF \Delta^{NVTAP}$ had stable disease after 21 weeks. In class 2 BRAF fusions there was significant activity to single agent MEK inhibitors. 4/6 patients had a treatment response to single agent trametinib. 2 with partial responses; one lasting 73 weeks and the other ongoing at 21 weeks. 2 with stable disease; one lasting 30 weeks and the other 12 weeks. In patients with class 2 BRAF in-frame deletions, 2 out of 5 had therapeutic responses. There was a partial response to single agent MEK inhibition lasting 24 weeks and stable disease on MEK and BRAF combination lasting 21 weeks and on-going. Patients with class 3 alterations did not derive benefit form BRAF targeted therapy in our cohort (N=3).

Figure 2. Therapeutic activity of BRAF targeted agents. Responses to 17 patients treated with BRAF directed therapy categorized by BRAF class, including 6 patients treated with combination BRAF and MEK and 8 patients with MEK inhibitor therapy alone. Each horizontal bar represents the time on therapy. Green bars represent patients with partial response as best response, light green are patients with stable disease, copper bars are patients with no response, and white bars indicate unevaluable subjects. Arrows indicate that patients continue on therapy.

1.16 Patients receiving BRAF directed therapy have improved outcomes

Using a multivariate model including BRAF alteration type, we compared overall survival between *patients with BRAF* alterations (delineated by BRAF subclass) who received a molecularly-matched therapy targeting the MAPK signaling pathway (e.g. a BRAF, pan-RAF, MEK, or ERK inhibitor) vs patients with *BRAF* alterations did not. There was a significant survival benefit, matched vs unmatched: (p = 0.02068, HR = 0.36 [0.15-0.86]). The extent of the survival benefits with targeted BRAF therapy were associated with functional class.

Overall survival analyses comparing patients with BRAF alterations (delineated by BRAF subclass) who received a molecularly-matched therapy (any treatment setting) targeting the MAPK signaling pathway (e.g. a BRAF, pan-RAF, MEK, or ERK inhibitor) vs patients with BRAF alterations (delineated by BRAF subclass) who did not. Matched Therapy vs Unmatched: 0.02068 (0.36 [0.15-0.86])

OS since Initial Diagnosis for the Advanced Cohort Class 1 (V600), matched (mOS=2.23, n=3) Class 1 (V600), unmatched (mOS=0.55, n=5) Class 2 (Fusion), matched (mOS=2.44, n=6) Class 2 (Fusion), unmatched (mOS=1.51, n=12) Class 2 (non-V600), matched (mOS=1.36, n=6) Class 2 (non-V600), unmatched (mOS=0.98, n=6) Other, matched (mOS=2.02, n=2) Other, unmatched (mOS=1.17, n=12)

Figure 3. Overall survival of pancreatic cancers with BRAF alterations

2.0 Goals

2.1 Primary Goal

To determine the efficacy of the combination of binimetinib and encorafenib as $\geq 2nd$ line of treatment for patients with metastatic pancreatic cancer with BRAF^{V600E} mutation.

- 2.11 Primary Endpoint Objective response rate at 24 weeks post-registration, as defined by RECIST 1.1.
- 2.2 Secondary Goals To determine in patients treated with the combination of binimetinib and encorafenib as ≥ 2nd line of treatment for patients with metastatic pancreatic cancer with BRAF^{V600E} mutation:
 - 2.21 The median progression-free survival Endpoint: The median time from study registration to clinical or radiographic disease progression or death, whichever occurs first, as defined by RECIST 1.1.
 - 2.22 The median overall survival Endpoint: The median time from study registration to death.
 - 2.23 Duration of Response Endpoint: The median duration of time from first documentation of an objective response to the earliest date progression is documented.
 - 2.24 Time to Response Endpoint: The median duration of time from study registration to the first documentation of an objective response.
 - 2.25 The safety and tolerability Endpoint: The rate of grade 3+ Adverse Events as defined by NIH CTCAE v5.0.
- 2.3 Correlative Research Goal
 - 2.31 To determine the mechanisms of resistance, either primary or acquired through real time monitoring of the BRAF mutational profile evolution.
 - 2.32 Endpoint: Additional mutations in BRAF or in other related genes as determined by nextgeneration sequencing from plasma samples.

3.0 Patient Eligibility NOTE: Waivers to eligibility criteria are not allowed per ACCRU policy

- 3.1 Pre-registration Inclusion Criteria
 - 3.11 Age ≥ 18 years.
 - 3.12 Histological confirmation of a pancreatic malignancy as confirmed by the local pathology lab

- 3.13 Patients whose disease has progressed on (or who were intolerant of) at least one line of therapy for metastatic disease
- 3.14 Patients whose disease has recurred with metastatic disease ≤12 weeks of completion of neoadjuvant or adjuvant systemic chemotherapy; or patients with locally advanced disease whose disease progressed to metastatic disease on, or ≤12 weeks after completion of systemic chemotherapy would also be eligible
- 3.15 Provide informed written consent ≤ 28 days prior to pre-registration.
- 3.16 Central electronic/paper confirmation of the presence of a BRAF^{V600E} mutation (Section 6.16). This review is mandatory prior to pre-registration to confirm eligibility.

Results from a CLIA/CAP certified testing lab (commercial or institutional) that confirm the presence of a $BRAF^{V600E}$ mutation in the patient's tumor must be submitted for central review.

3.2 Registration – Inclusion Criteria

NOTE: Registration must occur \leq 30 days after pre-registration.

- 3.21 Confirmation of the presence of $BRAF^{V600E}$ mutation in the patient's tumor (Section 6.2).
- 3.22 Measurable disease as defined in Section 11.0.
- 3.23 ECOG Performance Status (PS) 0, 1, or 2. (Form is available on the ACCRU web site)
- 3.24 The following laboratory values obtained \leq 14 days prior to registration.

NOTE: If your site laboratory reports use different units of measurements than what is required by the protocol eligibility requirements, please use the "Lab Test Unit Conversion Worksheet" available on the ACCRU website under "General Forms".

- Absolute neutrophil count (ANC) $\geq 1500/\text{mm}^3$
- Platelet count \geq 75,000/mm³
- Hemoglobin $\geq 9.0 \text{ g/dL}$
- Total bilirubin ≤ 1.5 x upper limit of normal (ULN)
- Aspartate transaminase (AST) ≤ 2.5 x ULN; in participants with liver metastases ≤5 x ULN
- Aminotransferase (ALT) \leq 2.5 x ULN; in participants with liver metastases \leq 5 x ULN
- Calculated creatinine clearance must be ≥45 ml/min using the Cockcroft-Gault formula below:

Cockcroft-Gault Equation :	
Creatinine clearance for males =	(140 - age)(weight in kg) (72)(serum creatinine in mg/dL)
Creatinine clearance for females =	(140 - age)(weight in kg)(0.85) (72)(serum creatinine in mg/dL)

- 3.25 Negative pregnancy test done \leq 7 days prior to registration, for women of childbearing potential only.
- 3.26 Willing to return to enrolling institution for follow-up (during the Active Monitoring Phase of the study).

Note: During the **Active Monitoring** Phase of a study (i.e., active treatment), participants must be willing to return to the consenting institution for follow-up.

- 3.27 Ability to swallow the investigational product tablets and capsules.
- 3.28 Willing to provide tissue and blood samples for correlative research purposes (see Sections 6.0, 14.0 and 17.0).
- 3.3 Registration Exclusion Criteria
 - 3.31 Patients whose tumor harbors a *BRAF non-V600E* mutation or a BRAF fusion.
 - 3.32 Prior therapy with BRAF inhibitor (e.g., encorafenib, dabrafenib, vemurafenib) and/or a MEK inhibitor (e.g., binimetinib, trametinib, cobimetinib).
 - 3.33 Known hypersensitivity or contraindication to any component of binimetinib or encorafenib or their excipients.
 - 3.34 Any of the following because this study involves an investigational agent whose genotoxic, mutagenic and teratogenic effects on the developing fetus and newborn are unknown:
 - Pregnant women
 - Nursing women
 - Men or women of childbearing potential who are unwilling to employ adequate contraception

NOTE: Female participants of childbearing potential must agree to use methods of contraception that are highly effective or acceptable, as described in Appendix II, and to not donate ova from Screening until 30 days after the last dose of study drug.

NOTE: Male participants must agree to use methods of contraception that are highly effective or acceptable, as described in Appendix II, and to not donate sperm from Screening until 90 days after the last dose of study drug.

- 3.35 Co-morbid systemic illnesses or other severe concurrent disease which, in the judgment of the investigator, would make the patient inappropriate for entry into this study or interfere significantly with the proper assessment of safety and toxicity of the prescribed regimens.
- 3.36 Immunocompromised patients and patients known to be HIV positive and currently receiving antiretroviral therapy. NOTE: Patients known to be HIV positive, but without clinical evidence of an immunocompromised state, are eligible for this trial.
- 3.37 Uncontrolled intercurrent illness including, but not limited to, ongoing or active infection, symptomatic congestive heart failure, cardiac arrhythmia, or psychiatric illness/social situations that would limit compliance with study requirements.
- 3.38 History of acute coronary syndromes (including myocardial infarction, unstable angina, coronary artery bypass grafting, coronary angioplasty or stenting) < 6 months prior to registration.
- 3.39a Left ventricular ejection fraction (LVEF) ≤50% as determined by MUGA or ECHO.
- 3.39b Uncontrolled hypertension defined as persistent systolic blood pressure \geq 150/100 mmHg or diastolic blood pressure \geq 100 mmHg despite current therapy.
- 3.39c Triplicate average baseline QTc interval \geq 480 ms.
- 3.39d Receiving any other investigational agent which would be considered as a treatment for the primary neoplasm.
- 3.39e Patients who have had another active malignancy within the past two years are ineligible EXCEPT FOR patients with cervical cancer in situ, in situ carcinoma of the bladder, non-melanoma carcinoma of the skin, or patients who have had therapy with curative intent for breast or prostate cancer, but remain on adjuvant hormonal therapy.
- 3.39f Received anticancer therapy including chemotherapy, immunotherapy, or antineoplastic biologic therapy (e.g., erlotinib, cetuximab, bevacizumab etc.), ≤ 14 days (≤ 28 days for an antibody-based therapy) prior to registration.
- 3.39g Patients who have undergone major surgery (e.g., in-patient procedures) ≤ 6 weeks prior to registration or who have not recovered from side effects of such procedure.
- 3.39h Patients who have had radiotherapy ≤14 days prior to registration or who have not recovered from side effects of such procedure. NOTE: Palliative radiation therapy must be complete 7 days prior to the first dose of study treatment.
- 3.39i Patient has not recovered to \leq Grade 1 from toxic effects of prior therapy before registration.

EXCEPTIONS: Stable chronic conditions (\leq Grade 2) that are not expected to resolve (such as neuropathy, myalgia, alopecia, prior therapy-related endocrinopathies).

3.39j Uncontrolled or symptomatic brain metastases or leptomeningeal carcinomatosis that are not stable, require steroids, are potentially life-threatening or have required radiation ≤28 days prior to registration.

NOTE: Patients with previously treated brain metastases may participate provided they are stable (e.g., without evidence of progression by radiographic imaging for ≤ 28 days prior to registration and neurologic symptoms have returned to baseline), and have no evidence of new or enlarging brain metastases or CNS edema, and does not require steroids at least 7 days before the first dose of study treatment.

- 3.39k Impairment of gastrointestinal function or disease which may significantly alter the absorption of study drug (e.g., active ulcerative disease, uncontrolled vomiting or diarrhea, malabsorption syndrome, small bowel resection with decreased intestinal absorption), or recent (≤12 weeks) history of a partial or complete bowel obstruction, or other condition that will interfere significantly with the absorption or oral drugs.
- 3.391 Known history of acute or chronic pancreatitis.
- 3.39m Concurrent neuromuscular disorder that is associated with elevated CK (e.g., inflammatory myopathies, muscular dystrophy, amytrophic lateral sclerosis, spinal muscular atrophy).
- 3.39n History or current evidence of RVO or current risk factors for RVO (e.g., uncontrolled glaucoma or ocular hypertension, history of hyperviscosity or hypercoagulability syndromes); history of retinal degenerative disease.
- 3.390 Current use of prohibited medication (including herbal medications, supplements, or foods), as described in Section 9.6, or use of prohibited medication \leq 7 days prior to registration.
- 3.39p History of thromboembolic or cerebrovascular events ≤ 12 weeks prior to registration. Examples include transient ischemic attacks, cerebrovascular accidents, hemodynamically significant (i.e. massive or sub-massive) deep vein thrombosis or pulmonary emboli.

NOTE: Patients with either deep vein thrombosis or pulmonary emobli that do not result in hemodynamic instability are allowed to enroll as long as they are on a stable dose of anticoagulants for ≤ 4 weeks prior to registration.

NOTE: Patients with thromboembolic events related to indwelling catheters or other procedures may register.

3.39q Evidence of Hepatitis B Virus (HBV) or Hepatitis C Virus (HCV) infection.

NOTE: Patients with laboratory evidence of cleared HBV or HCV infection may

register.

NOTE: Patients with no prior history of HBV infection who have been vaccinated against HBV and who have a positive antibody against hepatitis B surface antigen as the only evidence of prior exposure may register.

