4.0 Test Schedule

	Active Monitoring Phase						
Tests and procedures	≤28 Days Prior to Pre- reg	≤14 days prior to reg	Baseline (Prior to Cycle 1 Day 1 treatment)	C1D15 ±3 days	C2 and Beyond (±5 days)	At PD, withdrawal, or removal	30 Days after last dose
History and exam, weight, ECOG PS		X		Х	Х	Х	Х
Height		Х					
Adverse event assessment				Х	Х	Х	Х
Informed Consent	Х						
ECHO/MUGA ^{R, 9}		Х			Х	Х	
Hematology: CBC/ differential		X	Х	Х	Х	Х	Х
Chemistry: AST, ALT, alk phos, T. bili, creatinine, calcium, glucose, Na, K		X	Х	Х	Х	X	Х
CPK and troponin ¹⁰			Х		Х		
Ophthalmic exam ^{R, 5, 6}		Х					
Imaging (CT/PET CT or MRI) and tumor measurement ¹		Х			X^4	X	
Urine pregnancy test ²		Х					
Central electronic/paper confirmation of a $BRAF^{V600E}$ mutation ⁷	Х						
Mandatory tissue sample (see Section 17.0) ^{R,8}			X				
Mandatory blood sample (see Section 14.0) ^R			Х		Х	Х	
Patient Medication Diary (Appendix I) ³				X	X	Х	

1 CT scans – chest, abdomen, and pelvis with IV and PO contrast; in the case of iodine contrast allergies an MRI of the abdomen and pelvis with gadolinium + a non-contrast chest CT is appropriate. Use same imaging throughout the study. Imaging at PD should only be repeated if not done within 28 days prior.

2 For women of childbearing potential only. Must be done \leq 7 days prior to registration.

3 The diary must begin the day the patient starts taking the medication and must be completed per protocol and returned at the end of every cycle to the treating institution.

4 To be completed prior to cycle 2 and prior to 3^{rd} cycle and subsequent odd cycles (± 5 days)

- 5 A full ophthalmic exam will be performed by an ophthalmologist at screening, and as needed during on-study treatment phase and include best corrected visual acuity, slit lamp examination, intraocular pressure, dilated fundoscopy and Ocular Coherence Tomography (OCT). Examination of the retina is required, especially to identify findings associated with serous retinopathy and RVO.
- 6 After baseline, patients receiving **binimetinib** should be assessed at every physical examination for decreased visual acuity using a gross perimetry test (as opposed to automated visual field testing). Symptomatic patients should be referred for a full ophthalmic consultation.

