- 7 Results from a CLIA/CAP certified testing lab (commercial or institutional) that confirm the presence of a $BRAF^{V600E}$ mutation in the patient's tumor must be submitted for central review after the patient is pre-registered. See section 6.16 for detailed instructions.
- 8 Receipt of archival tumor tissue is not required for study registration and initiation of therapy. However, it is mandatory to receive the required tissue within 30 days from registration. See section 17.0.
- 9 ECHO/MUGA scans are to be performed at screening, on Cycle 2 Day 1, then every 12 weeks and at the end of treatment.
- 10 CPK and Troponin levels to be completed Cycle 1 Day 1 and Cycle 2 Day 1.
- R Research funded (see Section 19.0)

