- Contact the ACCRU Registration Office **Contact** If the patient was pre-registered, the ACCRU Registration Office staff can access the information from the centralized database and confirm the registration.
- Refer to "Application Training" at click on "Registration, Installation & Entry Instructions".
- 6.22 Correlative Research

A mandatory correlative research component is part of this study, the patient will be automatically registered onto this component (see Sections 3.0, 14.0 and 17.0).

- 6.23 Prior to accepting the registration, the registration/randomization application will verify the following:
 - Patient eligibility
- 6.24 At the time of registration, the following will be recorded:
 - Patient has/has not given permission to store and use his/her blood sample(s) for future research to learn about, prevent, or treat cancer.
 - Patient has/has not given permission to store and use his/her blood sample(s) for future research to learn, prevent, or treat other health problems (for example: diabetes, Alzheimer's disease, or heart disease).
 - Patient has/has not given permission to store and use his/her tissue sample(s) for future research to learn about, prevent, or treat cancer.
 - Patient has/has not given permission to store and use his/her tissue sample(s) for future research to learn, prevent, or treat other health problems (for example: diabetes, Alzheimer's disease, or heart disease).
 - Patient has/has not given permission for ACCRU to give his/her sample(s) to outside researchers.
- 6.25 Treatment on this protocol must commence at an ACCRU institution under the supervision of a medical oncologist.
- 6.26 Treatment cannot begin prior to registration and must begin ≤14 days after registration.
- 6.27 Pretreatment tests/procedures (see Section 4.0) must be completed within the guidelines specified on the test schedule.
- 6.28 All required baseline symptoms (see Section 10.3) must be documented and graded.
- 6.29a Blood draw kit is available on site.

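### The only scheduled pregnancy test is timed to registration, so a negative result can be 0 to 21 days old at first dose; a cheap re-check before dosing would close the gap

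*Combined protocol and SAP*

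**What the plan says.** Section 3.25 makes a negative pregnancy test a registration criterion, to be done no more than "7 days prior to registration, for women of childbearing potential only". Footnote 2 of the Test Schedule (Section 4.0) repeats the limit: "For women of childbearing potential only. Must be done" no more than 7 days before registration. The urine pregnancy row carries a single mark, in the pre-registration screening column. There is none in the column headed "Baseline (Prior to Cycle 1 Day 1 treatment)", and none at any later visit.

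Section 6.26 sets the start of dosing: "Treatment cannot begin prior to registration and must begin" within 14 days after it. Section 6.27 makes the schedule binding: "Pretreatment tests/procedures (see Section 4.0) must be completed within the guidelines specified on the test schedule".

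Other items are timed to first dose or Cycle 1 Day 1. Blood count and chemistry, already required before registration, are repeated at baseline. Footnote 10 reads "CPK and Troponin levels to be completed Cycle 1 Day 1 and Cycle 2 Day 1". Section 3.39h says "Palliative radiation therapy must be complete 7 days prior to the first dose of study treatment".

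Pregnant women are excluded under 3.34 because fetal effects are described as unknown. Contraception is required from Screening (3.34, Appendix II), including at least one non-hormonal method (9.5). Section 10.523 stops study drug at once if a patient becomes pregnant.

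**The concern.** The hazard named in 3.34 begins with the first dose, but the one scheduled test is counted back from registration. A pregnancy that arose between the test and the first dose, or was too early to show at the test, would not be looked for again before exposure. Section 10.523 says what to do once a pregnancy is known, but no scheduled test would reveal one.

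What is at stake is fetal safety in a very small number of women. Response rate, type 1 error, power and accrual targets are untouched.

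**Working it through.** The plan states no test-to-dose interval, so there is no figure to reproduce. The interval follows from two stated windows.

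**Inputs**
- Test to registration: 0 to 7 days (3.25; Test Schedule footnote 2).
- Registration to first dose: 0 to 14 days (6.26).

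**Age of the negative result at first dose** = (test to registration) + (registration to first dose)
- Minimum: 0 + 0 = 0 days.
- Maximum: 7 + 14 = 21 days.
- If both timings were spread evenly over the allowed days (an assumption), the mean would be 3.5 + 7 = 10.5 days.

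This does not depend on where the mark sits in the extracted table, because 3.25 and footnote 2 both tie the test to registration in words.

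**With a limit of 7 days before first dose**
- The age of the result becomes 0 to 7 days.
- Count the pairs (t days before registration, d days after) that already satisfy t + d ≤ 7. Out of 8 × 15 = 120 combinations, 8 + 7 + 6 + 5 + 4 + 3 + 2 + 1 = 36 do, or 30%. Under the same even-spread assumption, about 30% of affected women would need no second test.

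**How many women might be affected**
- Maximum accrual is 29 (16.22).
- Share of women in the retrospective series (1.14): 40/81 = 49.4% for all BRAF alterations, giving 0.494 × 29 = 14.3; and 13/17 = 76.5% for V600E, giving 0.765 × 29 = 22.2. So roughly 14 to 22 women.
- The documents do not give the share of childbearing potential. Median age was 64 (range 42 to 86) in the whole series and 63 for V600E. Assuming 0 to 15% of women, the count is 0 to 2.1 (of 14.3) or 0 to 3.3 (of 22.2), that is, about 0 to 3 patients.

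**What is not computed.** Turning days into expected pregnancies would need a contraceptive failure rate for these women and the detection delay of a urine test. Appendix II gives only a dividing line of 1% per year between its two classes of method, and no detection delay appears anywhere. No risk figure is therefore offered.

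**The case against.** The strongest reply has four parts.

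**The existing test does precede dosing.** It must be done before registration, and treatment cannot start before registration. That is right. A reader might infer that women reach first dose with no prior test; the documents do not support this. The accurate statement is only that no test is timed to first dose.

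**The risk is tiny and already managed.** Contraception is required from Screening. Appendix II asks for highly effective methods where mandated locally or where the investigator doubts compliance. Section 10.523 requires immediate discontinuation, with reporting and follow-up of any pregnancy. This stands as to size. It does not supply a check of status at first exposure: Appendix II also accepts methods with failure rates above 1% per year, and the protocol itself does not treat a promise of contraception as enough, since it also asks for a test.

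**Treatment can run for 36 cycles of 28 days (36 × 28 = 1,008 days) with no further scheduled test**, so one more test covers a short part of the risk period. That is fair, and it limits what the change achieves. First dose is still the one point at which exposure can be avoided altogether, at a visit where blood is already drawn.

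**Timing to registration is normal in this protocol.** Eligibility laboratory values, prior therapy and surgery are all counted that way. This stands too: 3.25 does its job as a registration criterion, and no internal contradiction is alleged.

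A reader might also infer that shortening the maximum from 21 to 7 days cuts the risk by two thirds. That does not follow. The age of a result is not the same as the chance of an undetected pregnancy, because a urine test may miss a very recent conception.

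**Conclusion.** The point holds as a small, cheap safety improvement. The interval of 0 to 21 days is certain, since it is the sum of two stated windows. The number of women affected rests on an assumed childbearing share of 0 to 15% and on a retrospective series resembling the trial population; on that basis it is about 0 to 3 of at most 29 patients, and quite possibly none. The absolute risk is very small and is not quantified here. No endpoint, error rate or power figure changes. The plan is not in error. The case for acting rests on the possible seriousness for an exposed fetus set against a very low cost.

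**What to change.** 1. Leave 3.25 as it is. Section 6.23 says "Prior to accepting the registration, the registration/randomization application will verify the following" and lists eligibility, and 13.6 judges eligibility as of registration, so a later result does not belong there.
2. In the Test Schedule, mark the urine pregnancy test in the existing baseline column before Cycle 1 Day 1.
3. That column gives no day window, so add to footnote 2: women of childbearing potential need a negative result no more than 7 days before the first dose; the registration test counts if it is still in window.
4. A patient who tests positive is not treated. Section 13.8 already classes anyone removed before treatment as a *cancel*. She is not evaluable under 16.21, which requires some protocol treatment, and the 3 extra patients in 16.22 already allow for cancellation.

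Cost: one mark in the table, one sentence in the footnote, at most one extra urine test per affected woman, and a small added step before first dose.
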